3.2 Aims and Objectives

The three specific aims will be realized in the context of the logic model shown in Fig. 3:

AIM 1: Assess the comparative effectiveness of two effective encounter decision aids (Option Grid and Picture Option Grid) against usual care on shared decision-making (SDM), decision quality, treatment choice and other direct outcomes in women, and differentially by socioeconomic status (SES).

Hypothesis 1. The encounter decision aids will increase SDM in the clinic visit and improve decision quality, knowledge, and quality of life in women of higher and lower SES compared to usual care. We also anticipate that they will reduce decision regret and improve the perceived integration of healthcare delivery (see Fig. 3).

Hypothesis 2. The Picture Option Grid will be more effective than the Option Grid at improving primary and secondary outcomes in women of lower SES. There will be no difference between the effects of the two encounter decision aids in women of higher SES.

AIM 2: Measure the effect of the Picture Option Grid on disparities in decision-making (decision quality, knowledge, and SDM) and treatment choice, and conduct an exploratory analysis of the mediation and moderation effects.

Hypothesis 1. Compared to the Option Grid and usual care arms, the Picture Option Grid will reduce disparities in decision quality, knowledge and participation in shared decision-making between women of lower and higher SES. It is also likely to reduce disparities in treatment choice.

Hypothesis 2. The effect of the Picture Option Grid on treatment choice will be mediated by post-intervention knowledge, shared decision-making, and post-intervention values (reported in 'What Matters Most to You' subscale of DQI, e.g., keeping breast, removing breast to gain peace of mind, avoiding radiation, etc.) (see Fig. 4).

[figure not shown]
Hypothesis 3. For women of lower SES, socioeconomic barriers (e.g., resource constraints, as reported in the Decision Quality Instrument) will affect treatment choice and thereby moderate the intervention's effect.

AIM 3: Explore strategies that promote the encounter decision aids' sustained use and dissemination using a theoretical implementation model.

Hypothesis 1. Pre-visit planning, minimal clinician training, flexibility of use, and integration into the workflow and EMR will facilitate sustained use.

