4.8 Analysis

4.8.1 Power Calculation

For Aim 1, hypothesis 1, we base the effect size estimation on published data from randomized controlled trials of decision aids for breast cancer surgery^{32,41,115,116}, suggesting that a reasonable effect size for DQI is 9.34, that the standard deviation between patients in the intervention arms compared to usual care is 12.00, and that a within-physician intra-class correlation (ICC) of 0.05 is reasonable. This ICC is justified because treatment varies within clinic, thereby allowing heterogeneity that occurs between physicians across centers to be blocked. We assume that four physicians will participate in the study at each of the four clinics (at least one assigned to each of the three trial arms at each center) and assume a patient attrition rate of 20%. Under these assumptions, a study of 1,100 participants (68.75 participants per physicians and 366.66 per treatment group) has power of greater than 99.8%

to reject the null hypothesis that the encounter decision aid groups and the control group have equal means, using a two-sided 0.05 level test when the true mean difference is 9.34. Given recruitment difficulties due to seasonal trends in breast cancer diagnoses and a lower number of eligible patients than planned based on the feasibility assessments (see reasons in modification letter), the sample size has been revised to 600 participants. The power will remain above 80% for all primary hypotheses.

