A crucial feature of this power calculation is that the design-effect equals 4.04, implying that approximately 4 times as many patients are needed to obtain the same power as for a study with patient-level randomization. Power remains above the traditional 80% threshold with an ICC greater than 0.19, implying that the power remains adequate even if the level of clustering of patients within physicians is greater than anticipated. Further, the attrition rate of 20% is expected to be an overestimate given the brevity of the trial. The standard deviation between patients' DQI values deliberately errs on the side of an overestimate; hence, power may be substantially greater. For hypothesis 2, we are basing the effect size estimation on the comparison between Picture Option Grid and Option Grid in women of lower SES. Because we anticipate obtaining a similar number of women in the higher and lower SES categories, the same power calculation is performed on a sample size of half the size. With 550 patients in total (34.375 patients on average per physician), under the same assumptions as above, the power for this subgroup test is 99% with ICC = 0.05 and 80% with ICC = 0.175.

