For Aim 2, the power of the test for disparities between higher and lower SES is necessarily lower than the overall test at the same effect size, as four groups are compared (Picture Option Grid higher SES, Picture Option Grid lower SES, Option Grid and usual care higher SES, Option Grid and usual care lower SES). However, because patient SES varies within physician, power can be conservatively computed as if the patient-level variance was doubled and the total number of patients halved. If the true difference in the effect of the Picture Option Grid on DQI between the higher and lower SES groups is 8.5 compared to Option Grid or compared to usual care, the power for a two-sided alpha-level test at the 0.05-level is just above 80%. With a revised sample size of 600 participants, the power is unlikely to reach 80%. However, given those power calculations are resting on assumptions that may not be entirely accurate, we will know once we start the analysis if we have enough power for aim 2 hypotheses with a sample size of 600 participants. A significant finding is even more likely to be obtained if the estimated variability in the data turns out to be much smaller than assumed here. It could indeed be the case with the revised sample size. It is not critical to account for multiple testing because in both the primary (Aim 1) and secondary (Aim 2) analyses, a single pair of groups is compared.

We are assuming an effect size of 9.34 based on past studies of decision aids for breast cancer surgery^{32,41,115}.

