As mentioned above, insurance status will be used to screen for higher and lower SES groups and invite participants into the study. It is an accepted proxy for SES¹⁵. At baseline, we will also collect information about median household income and highest educational attainment. For each included participant, we will check whether income and education confirm the initial screening allocation to higher or lower SES group or whether the patient belongs to the other group. The three measures of baseline socio-economic status: (1) insurance status, (2) highest educational attainment, and (3) median household income, will be analyzed separately for a multiple informants analysis¹²², or, provided they are not excessively collinear, we will enter them in the model together and test their combined effect. For income, we will use a poverty income ratio: the ratio of household income accounting for household size and poverty line published by the Census Bureau in the calendar year in which recruitment begins¹²³. To aid interpretation of our results, we will report the consequence of reassigning a patient from above median SES group to below median SES group, even if for added precision, it makes sense to base significance tests on continuous measures.

To gain insight into whether the Picture Option Grid and Option Grid will be more effective in certain subpopulations, we will add each SES measure and its interaction with the intervention indicator variables to the model. If the SES intervention interaction is non-significant, we will remove them from the model and test if the overall effect of SES is significant. Otherwise, we will perform stratified analyses of the interventions' effects by SES status.

4.8.4 Analyses Corresponding to Aim 2

Aim 2: Measure the effect of the Picture Option Grid on disparities in decision-making (decision quality, knowledge and shared decision-making) and treatment choice, and conduct an exploratory analysis of the mediation and moderation effects.

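### Aim 1 Hypothesis 2 (Picture vs Option Grid in lower-SES women) is powered as a direct subgroup test, but the only Aim 1 SES rule tests the interaction first, and the stated power is for 550 women, not about 300

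*Combined protocol and SAP*

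**What the plan says.** Section 3.2 states Aim 1 Hypothesis 2 in two parts: "The Picture Option Grid will be more effective than the Option Grid at improving primary and secondary outcomes in women of lower SES", and "There will be no difference between the effects of the two encounter decision aids in women of higher SES".

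Section 4.8.1 powers the first part. It says "we are basing the effect size estimation on the comparison between Picture Option Grid and Option Grid in women of lower SES", reruns the Hypothesis 1 calculation on half the sample (550 of 1,100), and concludes that "the power for this subgroup test is 99% with ICC = 0.05" and 80% at an ICC of 0.175. It mentions no interaction step. After the cut to 600 participants, the same section gives only a general assurance: "The power will remain above 80% for all primary hypotheses". Section 8.2.1 plans for about 300 lower-SES women.

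Section 4.8.3 holds the only Aim 1 rule for SES. Each SES measure and its interactions with the intervention indicators are added to the model. Then: "If the SES intervention interaction is non-significant, we will remove them from the model and test if the overall effect of SES is significant". Only in the other case are the intervention effects estimated by SES stratum. Section 4.8.8 describes the SES plans of Aims 1 and 2 in the same way, as interaction tests that decide whether subgroup analyses are done.

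**The concern.** The power section and the analysis section describe different procedures for the same hypothesis. If the interaction is non-significant and is removed, the Aim 1 model estimates one Picture-minus-Option difference averaged over SES. That is not the quantity in Hypothesis 2. If Hypothesis 2 were exactly true (9.34 in lower SES, 0 in higher SES, equal strata), the averaged difference would be (9.34 + 0)/2 = 4.67, half the lower-SES effect.

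Hypothesis 2 is the claim that tailoring helps the women for whom the Picture Option Grid was designed. A stated and powered hypothesis should have one test, fixed in advance, with a power figure for that test at the current sample size. Here neither the test nor the figure is settled.

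**Working it through.** **Inputs (4.8.1 unless noted).** Difference 9.34, SD 12, ICC 0.05, 16 surgeons (four at each of four sites), 20% attrition, three equal arms, two-sided 0.05. Lower-SES women: 550 in the stated calculation, about 300 in 8.2.1.

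**Formulas.** Completers per surgeon m = 0.8N/16. Design effect DE = 1 + (m − 1) × ICC. Completers per arm n = 0.8N/3. SE = 12 × √(2 × DE/n). Power = Φ(9.34/SE − 1.96).

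**Reproducing the plan (N = 550).** m = 27.5, n = 146.7.
- ICC 0.05: DE = 2.325, SE = 2.137, power 99.2% (stated 99%).
- ICC 0.175: DE = 5.64, SE = 3.327, power 80.2% (stated 80%).

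Both agree, so the stated power is that of an ungated two-arm test within the lower-SES stratum.

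**Same test at N = 300.** m = 15, n = 80.
- ICC 0.05: DE = 1.70, SE = 2.474, ratio 9.34/2.474 = 3.775, power 96.5%.
- ICC 0.175: DE = 3.45, SE = 3.524, power 75.5%.
- ICC at which power is 80%: about 0.149 (DE = 3.086, SE = 3.333).
- ICC 0.05 with a noncentral t on 13 df (16 surgeons minus 3 arms): 93.6%.
- ICC 0.05 with the Scheffé method of 4.8.3, taken as a 2-df critical value √5.99 = 2.448: Φ(3.775 − 2.448) = 90.8%, about 91%.

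**Interaction step, as an illustration only.** Take SES as binary, a single Picture-vs-Option interaction (1 df), and a true interaction of 9.34, meaning Hypothesis 2 is exactly true.
- The recipe in 4.8.1 for Aim 2 says "power can be conservatively computed as if the patient-level variance was doubled and the total number of patients halved", so the interaction SE is √2 times the stratum SE. Check at 1,100 with a difference of 8.5: √2 × 2.137 = 3.022, power 80.3%, which matches the plan's statement of just above 80%. At 600 with 9.34: √2 × 2.474 = 3.499, power 76.1%.
- If surgeon effects are fully shared across SES, they cancel from the interaction. With 80 completers in each of the four cells, SE = 12 × √(4 × 0.95/80) = 2.615, power 94.6%.

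The documents do not say how strongly surgeon effects are shared across SES, so they do not fix a value between these two.

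**Cost in precision of the stratum contrast.** Pooled over SES, there are 30 completers per surgeon and 160 per arm, DE = 1 + 29 × 0.05 = 2.45, and SE = 12 × √(2 × 2.45/160) = 2.10, against 2.47 in the lower-SES stratum alone.

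**The case against.** **The direct test may be what is meant.** Section 4.8.1 names the comparison, the population and the effect size. The rule in 4.8.3 is introduced as a way to learn about subpopulations, names no hypothesis and covers three SES measures, so it can be read as a supplementary effect-modification model. Section 4.8.8 calls its own analyses exploratory. This stands in part: the interaction-first reading is favoured but not certain. On the supplementary reading, however, the Aim 1 analysis section gives Hypothesis 2 no specified test.

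**Aim 2 may supply the comparison.** Section 4.8.4 compares the Picture Option Grid with the other arms within SES groups without an interaction gate, and the Aim 2 power text speaks of a difference "compared to Option Grid or compared to usual care". But this belongs to Aim 2. Its claim rule is a smaller SES effect under the Picture Option Grid, not the lower-SES Picture-minus-Option contrast, and it omits anxiety, regret and quality of life.

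**No shortfall in power is shown.** A reader might infer that Hypothesis 2 is underpowered at 600. The documents do not support that: the direct test has 96.5% power at ICC 0.05, so the general assurance of more than 80% holds for it. The ICC tolerance of about 0.15 is still three times the assumed value.

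**The gate figures are not the written gate.** A reader might also infer that the interaction-first route falls below 80%. The 76% rests on a recipe that the plan itself calls conservative. The rule in 4.8.3 involves interactions with both intervention indicators and several SES measures, and allows continuous SES. A 2-df joint test with binary SES and the same two variance assumptions gives 79% or 97% if the SES gap in usual care equals that in the Option Grid arm, and 66% or 90% if it lies midway between the two aid arms. The documents do not give that gap. This objection stands in full.

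**An interaction test guards against false subgroup claims.** True, and Hypothesis 2 has a differential part. The fix should keep the interaction in view.

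**Conclusion.** The point holds as a mismatch between the powered test and the written analysis rule, together with outdated power figures. Followed as written, 4.8.3 can leave a stated and powered hypothesis without an Aim 1 test, and the power in 4.8.1 does not describe that route. For about 300 lower-SES women the stated 99% and 80% become 96.5% and 75.5%, and the ICC giving 80% power falls from 0.175 to about 0.15. These figures rest on the plan's own effect size, SD, surgeon count and attrition, with equal arms and a normal approximation.

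Nothing here shows that the direct test is underpowered at the planned ICC. The power of the interaction-first route cannot be fixed from the documents; the range of about 76% to 95% only illustrates how much depends on an unstated assumption. It should be fixed before analysis, because two readings of the text lead to different tests. It would be wrong to infer that anyone intends to choose between them after seeing the data; the text merely does not exclude it.

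**What to change.** - In 4.8.3, state that Hypothesis 2 is tested as the Picture-minus-Option contrast in the insurance-defined lower-SES stratum, from a model that keeps the arm-by-SES terms whatever their p-value. This is the contrast that 4.8.1 already powers.
- Report the higher-SES contrast and the interaction beside it with confidence intervals. Any claim that the effect differs by SES should still rest on the interaction.
- In 4.8.1, restate the Hypothesis 2 power for about 300 women: about 96.5% unadjusted (94% with 13 df), about 91% if the 2-df Scheffé adjustment applies, and 80% at an ICC of about 0.15 unadjusted. Say whether the Scheffé adjustment covers this contrast.
- Keep interaction-first testing for the exploratory variables in 4.8.8, and reconcile 4.8.1, 4.8.3, 4.8.4 and 4.8.8.

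The cost is SAP wording and recalculated power figures. Statistically, the lower-SES estimate has a wider standard error than the SES-pooled one (about 2.47 against 2.10), and the interaction no longer screens this one pre-specified contrast.

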4.5.1 Primary Outcome Measure

The primary outcome measure (see Table 3) is the validated 16-item Decision Quality Instrument (DQI) for breast cancer (see Appendix C), which includes a knowledge subscale⁸⁹. The DQI, designed to be administered post-decision, will be assessed at T2 and T3. It aims to measure the extent to which patients are informed about their options, are involved in the decision-making process, and receive a surgery (mastectomy or BCS) aligned with their values, attitude towards risks, and preferences. It produces three scores: (1) knowledge, (2) concordance, and (3) decision process. Validation demonstrated good feasibility with minimal missing data and good 4-week retest reliability for both knowledge (ICC = 0.70) and concordance (ICC > 0.72). Discriminant validity was acceptable⁸⁹.

Table 3. Outcome Measures According to Data Collection Periods

	TIMEPOINT						
	-T0	T0 Baseline	T1 In-Visit	T2 Post- Visit	T3 1 wk PS*	T4 12 wks PS**	T5 1 yr PS
CONSENT AND ENROLLMENT							
Eligibility Screen	X						
Informed Consent	X						
Allocation (via surgeon confirmation)	X						
INTERVENTIONS							
Arm 1: Option Grid			X				
Arm 2: Picture Option Grid			X				
Arm 3: Usual Care			X				
OUTCOME MEASURES							
Rates of recruitment – documented and tracked in REDCap		X					
Discontinuation rates – documented and tracked in REDCap		X		X	X	X	X
Demographic data – 6 items, self-reported		X					
Health literacy – 1-item Chew's health literacy screening		X					
Decision quality (primary outcome measure) – validated 16-item DQI, subscale adapted for low SES				X	X		

Knowledge – validated 5-item DQI knowledge subscale		X		(X)	(X)		
Treatment intention – self-reported via DQI				(X)			
Treatment choice – obtained from medical records					X		
Quality of life – validated 6-item EQ-5D-5L		X				X	
Anxiety – validated 8-item PROMIS anxiety short form		X		X	X	X	
Shared decision-making (observed) – validated OPTION ⁵			X				
Shared decision-making (self-reported) – validated 3-item CollaboRATE				X			
Decision regret – validated 5-item decision regret scale					X	X	X
Integration of health care delivery – validated 4-item IntegRATE		X				X	
Financial toxicity – four items from validated COST measure and self-report of out-of-pocket medical expenses in the past month					X	X	X
Intervention's patterns of use – questions and photos of intervention				X	X		

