4.8.2 Analysis Plan

All data will be entered into REDCap, a secure research electronic data capture database (developed for the trial), and subsequently transferred to Stata for analysis. Initial examination of data will include descriptive statistics, frequency distributions, and histograms in order to identify outliers and missing data. All participants will be asked to indicate at T2 which

intervention they have received by being shown an image of each. Using this information, we will perform both an intention-to-treat and as-treated analysis.

4.8.3 Analysis Corresponding to Aim 1

Adapting the Decision Quality Instrument in Year 01.

We will use a two-step thematic analysis derived from descriptive phenomenology, assisted by the computer software ATLAS-ti. First, the transcripts will be coded to identify DQI items and instructions that require adaptation. In a second and more detailed analysis, the interview transcripts will be coded according to all the themes discussed in the interviews, including spontaneously emerging themes. Similar codes will be merged and subsequently grouped into families of codes and networks. Dual independent coding will be used for 100% of all interview transcripts, to ensure reliability of coding and to agree the themes and family of codes for all remaining interview transcripts. Discrepancies among raters will be discussed until agreement is reached.

Aim 1: Assess the comparative effectiveness of two effective encounter decision aids (Option Grid and Picture Option Grid) against usual care, on shared decision-making, decision quality, treatment choice and other direct outcomes in women, and differentially by SES.

We will first perform separate analyses for each follow-up period using linear and logistic regression models as appropriate for continuous (decision quality, SDM, quality of life, anxiety, decision regret, and IntegRATE) and binary (treatment choice) outcomes, respectively. The results will provide potentially valuable insights into how rapidly each intervention affects outcomes. Outcomes measured multiple times after T0 (anxiety, regret, decision quality, and financial toxicity) may also be analyzed using a longitudinal model. If the interventions are found to have an effect, a secondary analysis that adds predictors for the number of prior Option Grid and Picture Option Grid patients seen by the healthcare professional will examine whether there are physician learning effects under either intervention.

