We will adopt a regression framework for all analyses as it allows seamless transition between basic analyses involving a single predictor (or two indicators corresponding to each intervention versus the comparator) and more complex analyses involving additional predictors (mediation variables, control covariates, time-trends, interaction terms or effect modifiers). Further, the regression framework allows clustering of observations due to repeated measurements on patients across time, nesting of health professionals within sites, and patients within health professionals, to be accurately accounted for using mixed-effect regression models¹¹⁷ or generalized estimating equations^{118,119}. Multiple comparisons will be accounted for using Scheffe's method¹²⁰.

The secondary outcomes (SDM, anxiety, integration of healthcare delivery, decision regret, quality of life and financial toxicity) have in excess of 10 levels and will be analyzed as continuous variables. To assess whether the results of each analysis are trustworthy, we will analyze the residuals to check if the assumptions of the model hold¹²¹. For treatment choice, a clearly defined binary variable based on medical record data, we will adapt the model to a logistic regression model.

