A logistic regression model will be used to test for differences in decision quality, knowledge, participation in SDM, and treatment choice between the Picture Option Grid group and the usual care and Option Grid groups, within subpopulations (higher SES versus lower SES). A reduction of disparity due to the interventions will be claimed if the effect of SES on outcomes is significantly smaller for the Picture Option Grid group than for the other two groups at follow-up. As for Aim 1, a linear regression model will be used for the decision quality analysis while an analogous set of other predictors will be included as covariates in the model. The assumptions of the models will be evaluated for adequacy using residual analysis and other model fit diagnostics¹²¹. Our exploratory mediation analyses seek to identify and explicate the mechanism or process that underlies the relationship between the Picture Option Grid and a dependent variable via the inclusion of a third explanatory variable, known as a mediator variable (e.g., knowledge, values, SDM). We are specifically interested in whether interventions operate through the mediator as opposed to directly affecting the outcome. We will perform these analyses even if the findings from Aim 1 and Aim 2 (hypothesis 1) are non-significant in order to determine whether the null effect was due to a null effect of the intervention on the mediator or a null effect of the mediator on the outcome. To determine the generalizability of these mechanisms and identify subpopulations for whom mediation is most pronounced, we will compare the mediation effects across different subgroups (e.g., higher SES versus lower SES).

The traditional and often-used approach to estimating mediation effects is the causal steps approach, which originated in Baron and Kenny (1986)¹²⁴. However, due to the limitations of that approach, we will estimate the mediation effect using the product of coefficients method¹²⁵. Standard errors will be evaluated using the bootstrap¹²⁶ or the PRODCLIN program¹²⁷. Software exists for sensitivity analysis to violations of sequential ignorability and other assumptions required for causality in mediation analyses^{128,129}. We will apply this software and any additional procedures available to our analyses in order to obtain the most robust and defendable results.

4.8.5 Analyses Corresponding to Aim 3

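### Section 4.8.4 assigns logistic regression to three non-binary scores with no cut-point, contradicting the plan's linear models for decision quality and SDM and leaving the knowledge analysis undefined

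*Combined protocol and SAP*

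**What the plan says.** Section 4.8.4 (Aim 2) begins: "A logistic regression model will be used to test for differences in decision quality, knowledge, participation in SDM, and treatment choice". The comparison is between the Picture Option Grid arm and the other two arms, within SES groups. A reduction in disparity is to be claimed "if the effect of SES on outcomes is significantly smaller for the Picture Option Grid group than for the other two groups". The next sentence reads: "As for Aim 1, a linear regression model will be used for the decision quality analysis".

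Section 4.8.3 (Aim 1) classifies the outcomes differently. It plans "linear and logistic regression models as appropriate for continuous (decision quality, SDM, quality of life, anxiety, decision regret, and IntegRATE) and binary (treatment choice) outcomes". It then says that the secondary outcomes, a list that starts with SDM, "have in excess of 10 levels and will be analyzed as continuous variables". On the one binary outcome it says: "For treatment choice, a clearly defined binary variable based on medical record data, we will adapt the model to a logistic regression model". Neither list in Section 4.8.3 includes knowledge.

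Table 3 in Section 4.5.1 describes knowledge as the "validated 5-item DQI knowledge subscale". The plan states no scoring rule for it, and no threshold for decision quality, knowledge or SDM.

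**The concern.** A logistic model needs a binary, ordinal or binomial response. Of the four outcomes in the opening sentence of 4.8.4, the plan defines only treatment choice as binary. An analyst who follows that sentence must choose a cut-point, or a binomial or ordinal form, that the plan does not contain.

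Knowledge and SDM are both named in the disparity hypothesis of Aim 2 (Section 3.2, Aim 2, Hypothesis 1), so this touches outcomes on which a claim will be made. Three things are at stake:

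- **Precision.** Dichotomising a score discards information, and Section 4.8.1 already concedes that Aim 2 probably falls short of 80% power at 600 participants.
- **Pre-specification.** A cut-point chosen after the data are seen is a free choice inside the rule for claiming a reduced disparity.
- **Scale.** The claim is an interaction, and interactions depend on the scale. SDM would be reported as mean differences in Aim 1 and as odds ratios in Aim 2.

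**Working it through.** **Step 1. The text, outcome by outcome.**

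| Outcome | 4.8.3 (Aim 1) | 4.8.4, first sentence | 4.8.4, third sentence |
|---|---|---|---|
| Decision quality | continuous, linear | logistic | linear |
| SDM | continuous, linear | logistic | not mentioned |
| Knowledge | not listed | logistic | not mentioned |
| Treatment choice | binary, logistic | logistic | not mentioned |

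Decision quality is contradicted within 4.8.4, SDM between 4.8.4 and 4.8.3. Knowledge has one named model whose form is not defined. Treatment choice is consistent.

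**Step 2. Information kept after a cut, normal score, independent patients.** Relative efficiency = φ(z_p)² / [p(1−p)].

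- Median: 0.3989² / 0.25 = 0.637, a loss of 36.3%.
- 30/70 split: 0.576, a loss of 42.4%.
- 20/80 split: 0.490, a loss of 51.0%.

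**Step 3. A 5-item score.** Assume a binomial number correct with item success π. For a cut at k or more correct, the relative efficiency is [P′]² / [P(1−P)] divided by 5/[π(1−π)], where P = Pr(X ≥ k) and P′ is its derivative in π. At π = 0.5 and k = 3: P′ = 5 × 6 × 0.5⁴ = 1.875; 1.875² / 0.25 = 14.06; 5/0.25 = 20; ratio 0.703, a loss of 29.7%. The best cuts at π = 0.6, 0.7 and 0.8 lose 33.9%, 28.6% and 30.7%. Poor cuts lose far more, up to 99%.

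**Step 4. A score with a ceiling.** Assume a censored normal score cut at its maximum. The loss is 34% with 30% of patients at the ceiling, 13% with 50%, and about 4% with 60%. The documents give no distribution for knowledge or SDM, so none of these cases can be preferred.

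**Step 5. The plan's own Aim 2 power figure.** Inputs from Section 4.8.1: difference 8.5 DQI points, SD 12, ICC 0.05, 16 physicians (four at each of four clinics), 20% attrition, two-sided 0.05, patient variance doubled and N halved. Pairwise arms, normal approximation.

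- N = 1,100: 1,100 × 0.8 / 2 = 440, or 146.7 per arm and 27.5 per physician. Design effect 1 + 26.5 × 0.05 = 2.325. Effective n per arm 146.7/2.325 = 63.1. SE = 12√2 × √(2/63.1) = 3.02. Power = Φ(8.5/3.02 − 1.96) = 0.803. This reproduces the stated figure of slightly over 80%.
- N = 600: 240 patients, 80 per arm, 15 per physician. Design effect 1 + 14 × 0.05 = 1.70. Effective n 47.1. SE = 3.50. Power = Φ(8.5/3.50 − 1.96) = 0.681.

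**Step 6. The same test after a median split, N = 600.** With the same design effect: Φ(2.43 × √0.637 − 1.96) = 0.491. If the score is latent normal, the ICC of the binary variable falls to (2/π)·arcsin(0.05) = 0.032 (here π is the circle constant). The design effect is then 1 + 14 × 0.032 = 1.45, the net efficiency is 0.637 × 1.70/1.446 = 0.749, and power is 0.556. This is an illustration on DQI, the only score with planning inputs.

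**Step 7. Why the scale matters.** Take assumed success rates of 50% and 70% by SES in usual care, and 80% and 92% with the Picture Option Grid. The gap shrinks from 20 to 12 percentage points. The odds ratio rises from (0.70/0.30)/(0.50/0.50) = 2.33 to (0.92/0.08)/(0.80/0.20) = 2.88. The disparity narrows on one scale and widens on the other.

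**The case against.** The best defence is that this is a drafting slip which the rest of the plan corrects. Section 4.8.3 matches model to outcome type, 4.8.4 itself returns to linear regression for decision quality, and the Aim 2 power statement is in DQI points. For decision quality the defence succeeds in substance. A reader might infer that the primary disparity test cannot be run without a cut-point; the third sentence of 4.8.4 shows that it can.

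For SDM the defence is weaker. Section 4.8.4 is the specific text for Aim 2, and nothing in it restores the continuous analysis. For knowledge, one could argue that it is one of the three DQI scores (Section 4.5.1) and so falls under the decision quality analysis. But 4.8.4 lists the two side by side as separate outcomes, so that reading cannot be relied on. It is also true that a binomial logistic model on items correct, or an ordinal one, needs no cut-point. The plan names neither.

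Three stronger inferences are not supported:

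- **That a third or more of the information is always lost.** This holds for a normal score with independent patients. Steps 3, 4 and 6 give cases below one third.
- **That power falls from about 90% to 74% or 62%.** These values come from a purely within-surgeon contrast for one pair of arms, SE = √(4 × 144 × 0.95/80) = 2.615, with cuts at the median and the 80th percentile. They use DQI inputs for the one score already given a linear model, and the 90% baseline conflicts with the plan's own admission for N = 600. The contrast matters too: pooling Option Grid with usual care under the plan's rule gives 0.801 at N = 600, but 0.901 at N = 1,100, which does not match the stated figure. The pairwise form does.
- **That treatment choice must be reported as a difference in risk differences.** That is a preference about scale. Logistic regression for a binary outcome is consistent with Section 4.8.3 and is not an error.

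**Conclusion.** The point holds in a limited form and should be corrected before analysis. The opening sentence of 4.8.4 is wrong as written for decision quality and SDM, and incomplete for knowledge. The consequence depends on what an analyst does with it. If the sentence is ignored in favour of linear models, nothing is lost. If it is followed by dichotomising, precision drops by the amounts in Steps 2 to 4, and the SDM disparity claim moves to a different scale from Aim 1.

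No power loss can be stated for knowledge or SDM, because the documents give neither an SD nor an effect size for them. The fall from 68% to 49-56% shows only what a median split would do to DQI under the plan's own rule, assuming a normal score and pairwise arms; the upper value also assumes the smaller binary ICC. The textual contradiction is certain; its numerical cost is not.

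**What to change.** In Section 4.8.4, delete the assignment of logistic regression to decision quality, knowledge and SDM. State one model per outcome:

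- **Decision quality, knowledge and SDM scores:** linear models with arm-by-SES interaction terms, using the clustering of patients within health professionals that Section 4.8.3 already adopts for all analyses. The disparity claim then rests on the interaction in score points, the scale that Aim 1 uses for decision quality and SDM.
- **Treatment choice:** logistic regression, as now.

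Add knowledge to the list of continuous outcomes in 4.8.3, so that both aims treat it alike. If a binary, binomial or ordinal analysis of any score is wanted as well, name it as secondary and fix its form or cut-point before the data are seen.

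The cost is a change of wording. It needs no new data and no change to the sample size.
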